Liver injury may be caused by both the direct toxicity of alcohol metabolic by-products and the inflammation induced by the by-products themselves. Numerous studies showed that alcohol extended the hepatotoxicity caused by anti-TB drugs [93] [94] [95]. Even patients receiving rifampicin as a preventative treatment have been shown to be at risk [96] [97].

Concomitant Infection

It has been suggested that mild inflammatory reactions caused by co-existing viral infections can frequently function as a "danger signal", allowing the development of early events in the pathophysiological process into a full-blown hepatotoxic reaction; this can be explained by the increased level of drug hypersensitivity in these patients [98]. Several cohorts have been examined to determine whether chronic infections other than tuberculosis raise DILI risk during anti-TB therapy. The risks of drug- and virus-induced hepatitis were significantly higher in patients with high initial viral load than those with low initial viral load and those without viral hepatitis (39% vs 10.5% of HBV patients and 33% vs 16.7% of HCV patients, $p<0.001$) [99]. This study has also demonstrated a direct correlation between the viral load at the onset of anti-TB therapy and the severity of hepatotoxicity [99]. Comparable to HBV infection, 30% of all HCV-infected patients receiving anti-TB medication developed hepatotoxicity, whereas 11% of controls had a 5-fold relative risk of hepatotoxicity development and severity directly related to the viral load [100]. Additionally, there is a significant increased risk of hepatotoxicity from anti-TB drugs when HIV infection coexists. This has been observed both prior to and during the highly active HAART era. Hepatotoxicity ranged from 4 to 15% in the pre-HAART period and from 4 to 27% in the HAART era [101]. Nevertheless, a number of confounding factors have been identified, including the use of intravenous drugs, alcoholism, viral hepatitis, hepatotoxicity due to HAART therapy, drug-drug interactions, and liver damage caused by immune reconstitution [101].

Rationale and Aims

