Patient's susceptibility to DILI during treatment with anti-TB drugs is influenced by several drug- and host-related factors [102]. The most extensively studied potential causes of INH-induced DILI are related to those mechanisms. As to drug-related factors, acetylhydrazine, which is generated by NAT2, is widely considered as a crucial INH metabolite that contributes to INH-induced DILI. Given the importance of acetylation in INH metabolism, several studies have investigated into NAT2 loss of function polymorphisms as possible risk factors for DILI. In addition, advanced age [94], female gender [86], poor nutritional status [103], HBV or HCV infection [100] [104], HIV infection [78] [105], chronic liver disease, and alcoholism are environmental, physiological, and pathological factors contributing to DILI incidence. Moreover, the influencing variables differ according to racial and geographic characteristics.

Studies conducted in China demonstrated that approximately one-third of DILI patients had no symptoms, including some cases with severe liver injury [106] [107]. It has been demonstrated that screening patients for risk factors is useful in preventing disease progression, improving the outcome of therapy, and reducing mortality. However, rapid acetylators are very common in the Chinese population, so they are characterised by a lower susceptibility to develop DILI. Our patient cohort is multi-ethnic, with a prevalence of Caucasians and so a higher frequency of slow acetylator status. For this reason, our objective is to corroborate the conclusions drawn by the previous studies through the examination of our complementary data.

Outcome measures and assessments

The primary outcome is to determine the association between risk factors (drug- and host-related factors) and the incidence of DILI.

The primary outcome measures are the occurrence of anti-TB DILI (number of participants with DILI), which was defined by: 1) AST or ALT level > 5 times the ULN in patients with absence of symptoms or with total BIL level > 2 times the ULN, or 2) AST or ALT level > 3 times the ULN and total BIL level > 3 times the ULN in patients who show symptoms compatible with hepatitis.

The secondary outcome is to evaluate the characteristics of patients who first experienced anti-TB DILI. The secondary outcome measures are the prevalence of early hepatotoxicity experience.

Methods

Study design

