- Clinical data: age, weight, height, gender, ethnicity, hepatotoxicity or alcoholism, duration of anti-TB treatment, tuberculosis site (pulmonary or extra), adverse event, concomitant infection (HIV, HAV, HCV, HBV), past medical history, concomitant drugs. Patient's nutritional status was reported as BMI, which was calculated based on height and body weight;
- Biochemical data: ALT, AST, GGT and BIL;
- Laboratory data: NAT2 acetylator status. The acetylation status of patients will be assigned like as suggested by earlier research:
 - rapid acetylator: NAT2*4 is a wild-type allele (defined by absence of slow alleles);
 - intermediate acetylator status: carry one copy of NAT2*4 and one defective variant allele (NAT2*5, *6, *7, and *14);
 - slow acetylator: two copies of slow variant allele (NAT2*5, *6, *7, and *14).

Statistical analysis

Sample size calculation

[figure not shown]
We are planning a study of matched sets of cases and controls with 2 matched controls per case. Prior data indicate that the probability of exposure among controls is 50%, and the correlation coefficient for exposure between matched cases and controls is -0.2 [10] [108] [109] [110] [111]. If the true odds ratio for disease in exposed subjects relative to unexposed subjects is 3, we will need to study 40 case patients with 80 matched controls to be able to reject the null hypothesis that this

odds ratio equals 1 with a power of 80%, assuming that the Type I error probability associated with the test of this null hypothesis is 5%.

[figure not shown]
Parameters: Exposure in cases = 75%; Exposure in controls = 50%

Absolute difference = 25%; Relative difference = 50%; Odds ratio = 3

Sample sizes across range of OR and control exposure, with inputted values:

Number of cases required varying ratio of controls per case, other inputs constant:

We will use a nested case-control study design that takes into account time of events occurrence in sampling of controls. For each case, one or more controls are selected from the risk set at the time in which the event of interest occurred in the case. The risk set means the set of all individuals that are still “events-free” and not censored. Therefore, they are still included in the study at that time, thus, eligible to experience the event now observed in the case. As a consequence, individuals can

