The data collected will provide important new perspectives on the management and prevention of DILI. Preventing serious hepatic failure requires early detection and prompt drug withdrawal, which is also a crucial step in managing adverse reactions. The diagnosis of DILI is based on the index of suspicion, the careful assessment of the temporal correlation between the exposure to a specific drug and the particular clinical event, and the exclusion of other possible diagnoses.

For patients undergoing anti-TB treatment, hepatotoxic side effects represent significant obstacles. Indeed, DILI development can compromise treatment compliance, or lead to treatment interruption, or, again, result in disease relapse, or induce drug resistance; all these conditions will finally lead to treatment failure. Screening patients for risk factors is of great importance in preventing disease progression, improving therapeutic outcomes, and reducing mortality.

Furthermore, patient's re-exposure to the same drug regimen leads to DILI recurrence in 11%–30% of cases [112]. Compared with the initial event, DILI after rechallenge occurs more rapidly (generally after days or weeks) than after initial exposure [113]. DILI on rechallenge leads to jaundice in 64%, hospitalisation in 52%, and mortality in 13% of cases [114].

Combining host- and drug-related risk factors associated with the development of DILI might generate better tools to pre-empt or diagnose DILI, leading to better regimen tolerability and ultimately to a better treatment outcome.

Study Management & Coordination

PI with support from the working group's different specialists, is responsible for coordinating and accurately executing the study in compliance with the procedures outlined in this protocol. All study-related documentation (including protocol, amendments, eCRF, database, partial and final reports) must be archived by PI. Each component of documentation will be preserved electronically.

Study Timeline

The study will start after obtaining approval from the Ethical Committee. Consequently, the duration will be computed for a total of three months, starting from the approval of this study protocol.

Ethical Considerations

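### The DILI case definition has no step to exclude other causes, so viral or alcoholic liver injury arising on treatment counts as DILI while both are studied as risk factors

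*Protocol*

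**What the plan says.** Under Outcome measures and assessments, the Protocol gives two routes to being a case. The first is "AST or ALT level > 5 times the ULN in patients with absence of symptoms", or that enzyme level with total bilirubin above 2 times the ULN. The second is a transaminase above 3 times the ULN together with "total BIL level > 3 times the ULN in patients who show symptoms compatible with hepatitis". Neither route asks whether something other than the drugs explains the rise.

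The same section sets the aim: "The primary outcome is to determine the association between risk factors (drug- and host-related factors) and the incidence of DILI". Among those factors, Rationale and Aims states that "HBV or HCV infection [100] [104], HIV infection [78] [105], chronic liver disease, and alcoholism are environmental, physiological, and pathological factors contributing to DILI incidence". The list under Data collection takes in infection with HIV, HAV, HCV and HBV, and alcoholism. Its biochemistry consists of ALT, AST, GGT and bilirubin. It names no viral serology or viral load at the time of the event.

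Two other places bear on attribution. Potential Benefit of the Study says that the diagnosis of DILI depends on suspicion, on timing relative to the drug "and the exclusion of other possible diagnoses". The background section on concomitant infection reports a cited cohort in these terms: "The risks of drug- and virus-induced hepatitis were significantly higher in patients with high initial viral load".

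Study population requires normal ALT and bilirubin and no liver symptoms before treatment. It excludes prior liver dysfunction (biliary included), abnormal baseline hepatic tests and concomitant hepatotoxic drugs. It does not exclude patients with viral hepatitis or alcoholism whose baseline tests are normal.

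**The concern.** In a simple incidence count, a few events with another cause would add noise. Here the main question is which host factors go with DILI, and some of those factors can raise the same enzymes without any drug effect. The Protocol accepts this in its background sections: it speaks of virus-induced hepatitis and of direct liver injury from alcohol by-products.

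A carrier who enters with normal tests and flares in month two meets the definition, becomes an anti-TB DILI case, and counts as evidence that carriage is a risk factor for DILI. The same holds for alcoholic hepatitis or acute hepatitis A during treatment. This is outcome misclassification that depends on the exposure. Matching on age, sex and BMI does not remove it, and neither do larger numbers. For exposures unrelated to those events, NAT2 status for example, the extra cases pull the odds ratio towards 1.

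**Working it through.** **1. The passages side by side.**

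| Alternative explanation | Handled by the entry criteria or design? | Handled by the case definition? |
|---|---|---|
| Liver or biliary disease before treatment | Yes, excluded | – |
| Another hepatotoxic drug | Yes, excluded | – |
| Enzyme rise that predates treatment | Yes, normal baseline required | – |
| Flare on treatment in a carrier with normal baseline tests | No | No |
| Acute viral hepatitis on treatment | No | No |
| Alcoholic hepatitis on treatment | No | No |

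The gap is confined to the last three rows.

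**2. The plan's own figure.** Inputs from Sample size calculation: 2 controls per case (M = 2), control exposure 0.50, case exposure 0.75, OR ψ = 3, correlation −0.2, power 80%, alpha 5% (taken as two-sided). The Dupont formula for matched sets is n = [z(power)·√v(ψ) + z(1−α/2)·√v(1)]² / [e(1) − e(ψ)]², where t(k) is the probability term for k exposed members in a set, e(ψ) = Σ k·t(k)·ψ/(kψ + M − k + 1) and v(ψ) = Σ k·t(k)·ψ·(M − k + 1)/(kψ + M − k + 1)².

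- t(1) = 0.3433 and t(2) = 0.4833
- e(3) = 0.6202 and e(1) = 0.4366; v(3) = 0.1416 and v(1) = 0.1837
- n = (0.8416 × 0.3763 + 1.9600 × 0.4286)² / 0.1836² = 39.7

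If case exposure is solved from the matched OR instead, n = 40.2. The stated 40 cases and 80 controls reproduce.

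**3. Inflation of the viral association.** Let d be the risk of true drug injury, the same with and without infection (no true effect). Let f be the share of infected patients with a flare above threshold, independent of d. Then the risk in the infected is r = d + (1 − d)f, and the spurious OR is [r/(1 − r)] / [d/(1 − d)]. The range 5% to 28% for d comes from the Protocol's introduction. So does 11%, its figure for hepatotoxicity under combined INH, RMP and PZA. All values of f are assumptions, since the Protocol gives none.

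| d | f = 2% | f = 5% | f = 10% |
|---|---|---|---|
| 5% | 1.41 | 2.05 | 3.22 |
| 11% | 1.19 | 1.48 | 2.01 |
| 28% | 1.07 | 1.19 | 1.40 |

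Example: d = 5%, f = 10% gives r = 0.05 + 0.95 × 0.10 = 0.145, and (0.145/0.855)/(0.05/0.95) = 3.22.

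Controls are sampled from risk sets, so the study estimates a rate ratio, 1 + ln(1 − f)/ln(1 − d). This is a little lower: 2.00 and 3.05 at d = 5%, and 1.16 and 1.32 at d = 28%, for f = 5% and 10%.

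**4. Dilution of another association.** Let a share m of cases be non-drug events with 50% exposure. Case exposure becomes 0.75(1 − m) + 0.50m.

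- m = 10%: 0.725, OR = 0.725/0.275 = 2.64; the formula in step 2 then needs 49.6, about 50 cases
- m = 20%: 0.700, OR = 0.700/0.300 = 2.33; 63.4, about 64 cases

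The share m may well be smaller. With assumed values of 5% carriers, f = 10% and d = 10%, m = (0.05 × 0.90 × 0.10)/(0.10 + 0.0045) = 4.3%, and the OR falls only to about 2.8.

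**5. The opposite error.** If cases with a recorded viral cause are removed, and a share x of true drug injuries in carriers carries that label, the OR for infection is multiplied by (1 − x). At an assumed x = 30%, a true OR of 2 becomes 1.4, and a true OR of 1 becomes 0.7.

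**The case against.** The strongest reply is that a threshold definition is a legitimate choice. The introduction says that most published reports define hepatotoxicity in this way, the stated aim is to corroborate earlier studies, and the sentence on excluding other diagnoses stands in a section on benefit, where it describes clinical diagnosis. That supports keeping thresholds for the main analysis. It does not remove the problem, because viral infection and alcoholism are among the factors to be tested, and the same introduction concedes that it is hard to know how many such events fit the consensus definition of DILI.

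A reader might infer that the definition ignores timing. The documents do not support this: Study design concerns DILI arising during treatment, entry requires normal tests beforehand, and controls are sampled at the event time. A reader might also infer that laboratory values alone decide. Symptoms are part of both criteria, although symptoms of hepatitis do not separate viral from drug injury.

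A third tempting reading is that cases with an alternative cause should simply leave the primary case set. That selects cases on the exposure under study while exposed controls stay, with the effect in step 5 of the working. The Protocol itself presents viral infection as a possible trigger of drug injury, so records may not separate the two. This objection stands, and it shapes the fix.

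**Conclusion.** The point holds as a gap in attribution, limited to viral and alcoholic liver injury that arises on treatment. The direction is clear: upward for the viral and alcohol associations, and towards 1 for unrelated exposures such as NAT2.

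The size is not known. The Protocol gives neither the number of infected patients nor a flare rate. With flares in 5% to 10% of the infected, no true effect and independence of flare and drug injury, the spurious OR is about 1.2 to 1.4 at the top of the Protocol's incidence range and about 2.1 to 3.2 at the bottom. No comparable figure can be given for alcohol.

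Two further inferences go too far. The sample size is not wrong, since it reproduces. Nor should the spurious ORs be set against the OR of 3 used for sizing as if they concerned the same exposure: that calculation assumes 50% exposure in controls, and nothing ties it to viral infection.

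**What to change.** Keep the threshold-and-symptom definition for the main analysis, and add to the Protocol:

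- **Record.** For each case, abstract from the chart whether an alternative cause (acute or reactivated viral hepatitis, alcoholic hepatitis) is documented, excluded or not assessed. The abstractor should be blind to NAT2 status.
- **Analyse.** Pre-specify a sensitivity analysis without the cases that have a documented alternative cause, dropping each with its matched set. Show it with the not-assessed cases in and out.
- **Interpret.** Read the viral and alcohol associations as bounded by the two analyses. The main analysis can err upward, and the restricted one can err downward. The bracket concerns this source of error only and depends on how fully causes were worked up, which is why the not-assessed cases are shown both ways.

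The cost is one or two eCRF fields filled from existing records. The sensitivity analysis will hold fewer than the planned 40 cases and will be less precise. If work-up at the event was rarely recorded, the not-assessed group may be large; that would itself be worth reporting.

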Tuberculosis is the world's second leading cause of death from a single infectious agent in 2022, after COVID-19 [1]. In 2022, TB disease was estimated to affect 10.6 million people, from which 1.3 million died because of it, despite the WHO adoption of the End TB Strategy [1] [2]. The standardised therapy involves a treatment regimen of INH, RMP, PZA, EMB, for 2 months, then INH and RMP for at least an additional 4-7 months [3]. Even though 85% of TB cases are successfully treated, significant morbidity from treatment-related adverse events, such as hepatotoxicity, skin reactions, gastrointestinal, and neurological disorders, reduces the efficacy of therapy [4] [5] [6]. In 11% of patients receiving INH, RMP, and PZA in combination, hepatotoxicity is the most frequent adverse effect that results in drug discontinuation [5] [7] [8]. One of the most prevalent subtypes of idiosyncratic hepatotoxicity is caused by anti-TB drugs [4] [9] [10]. Numerous variables, including the features of the specific cohort, the drug regimens used, the employed threshold to define hepatotoxicity, and the monitoring and reporting procedures, influence the incidence of anti-TB drug-induced hepatotoxicity. Overall, 5%–28% of patients receiving anti-TB drugs have experienced hepatotoxicity associated with the drug [4] [10]. It is difficult to determine how many of these fit the recent international consensus definition of DILI [9]. The majority of reports have defined hepatotoxicity as an elevated level of AST or ALT that is three times the ULN when symptoms (such as abdominal pain, nausea, vomiting, unexplained fatigue, or jaundice) are present, or five times the ULN when symptoms are absent [5]. Up to 20% of patients receiving INH as monotherapy or combination therapy for TB may experience a transient, asymptomatic elevation in liver enzymes; however, it usually resolves without drug discontinuation [11] [12] [13]. ATDH may manifest as asymptomatic elevations in liver enzymes or even as fulminant liver failure [5] [14]. In accordance to these results, the most commonly observed DILI pattern is the hepatocellular one [15]. Anti-TB drugs related hepatotoxicity is of great concern not only because of its frequency but also because of its severity and outcome. The median interval between starting a course of anti-TB treatment and the onset of clinical symptoms is 16 weeks (range 6 weeks-6 months) [16] [17] [18]. Despite decades of use and a large number of patients exposed to anti-TB drugs worldwide, the pathogenesis underlying

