This is a retrospective observational study, no profit, to determine environmental, physiological, and pathological factors associated with the incidence of DILI during anti-TB treatment. Data collected from patients with confirmed tuberculosis, enrolled at the Department of Infectious Diseases of Luigi Sacco Hospital in Milan, Italy, between July 2020 and September 2023, will be analysed. Subjects were all followed up as outpatients at Tuberculosis Clinic at Luigi Sacco Hospital, some of them with previous inward stays at various hospitals in the Lombardy Region.

Study population

The following are the inclusion criteria: 1) adult patients (>18 years), 2) patient who received standard initial therapy including INH (5mg/kg), RMP (10mg/kg), and PZA (25mg/kg) for patients with active TB disease, 3) treatment with first line anti-TB drugs, including rifampicin and isoniazid for patients with latent TBI, 4) normal serum ALT and bilirubin levels, no symptoms related to abnormal liver function prior to anti-TB drug treatment and 5) informed consent. Patients with any of the following conditions are excluded from the study: 1) liver dysfunction, including biliary origin, before anti-TB therapy, 2) patients receiving non-standard treatment regimen initially (e.g., patients with severe pulmonary or extrapulmonary TB receiving large doses or more than four anti-TB drugs), 3) modified treatment regimen due to drug resistance or intolerance excluding first line anti-TB drugs, 4) lactation or pregnancy, 5) concomitant use of hepatotoxic drugs, 6) abnormal hepatic function on laboratory testing before anti-TB, 7) disease that was resistant to INH at the start of treatment or 8) patients refusing to sign informed consent.

The participants were given standard anti-TB treatment in line with international guidelines (RMP 10 mg/kg, INH 5 mg/kg), primarily administered orally, although intravenous administration was

employed for inpatients as needed, and modified to oral administration as soon as possible. The other drugs of the standard regimen included standard daily doses of PZA (15-30 mg/kg) and EMB (15-20 mg/kg).

Data collection

Data that will be collected include clinical, biochemical, and genotyping findings that are typically used in clinical practice to manage and monitor tuberculotic patients at Luigi Sacco Hospital. The complete list of parameters (host- and drug-related factors) is provided below:

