be sampled as controls for more than one case and, in turn, individuals sampled as controls may subsequently become cases. Cases and controls will be matched according to baseline variables, including age, sex, and BMI, and then conditional regression analysis (a type of matched statistical analysis) will be performed to draw associations.

Data management

All data are retrieved from the patient's medical record. Variables will be entered into the eCRF by site staff, who will be trained on how to use the eCRFs and capture the data required by the protocol. The eCRF is an electronic data entry media and should not constitute the original (or source) medical record. Data derived from source documents and reported in the eCRFs should be consistent with the source documents, or the discrepancies should be explained in these source documents. The investigator must complete the eCRF for each participant. The investigator's signature on the eCRF will attest to their accuracy and completeness.

Data collected from each participant will be anonymized: each subject will be assigned a unique code so that only the investigator will be able to identify the subject. The file associating the participant's code with their identifying data will be stored separately on a password protected computer. The study database will be password protected and uploaded to a computer that is also password protected and accessible only to study personnel designated by PI. Identification of the data will be done in such a way that individuals accessing the database will not be able to trace the identity of the subjects in any way.

The study will involve statistical calculations on collected data using literature standard methods to identify and correlate variables (Chi-square, Fisher's exact, Mann-Whitney U-test, conditional regression). The results will be published in medical journals and presented at conferences. Study data will be retained for 7 years starting from the study's conclusion. Data processing will be done in strict compliance with GDPR and any applicable national legislation.

Potential Benefit of the Study

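### Exclusion criterion 3 has no time limit, so in a retrospective chart review it can remove patients who were taken off first-line drugs because of DILI, the primary outcome

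*Protocol*

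**What the plan says.** Criterion 3 in the exclusion list (Protocol, Study population) reads "modified treatment regimen due to drug resistance or intolerance excluding first line anti-TB drugs". It has no time phrase, and no other section supplies one. Exclusions 1, 2, 6 and 7 in the same list are each tied to baseline or treatment start; exclusions 4 and 5 are not. Inclusion 2 already requires a "patient who received standard initial therapy including INH" with the other standard drugs for active disease, and inclusion 3 requires first-line drugs for latent infection.

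Under Study design: "This is a retrospective observational study". Data management adds that all data come from the medical record. Under Outcome measures and assessments: "The primary outcome measures are the occurrence of anti-TB DILI (number of participants with DILI", followed by the laboratory definition.

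The Statistical analysis section plans a nested case-control study. Members of a risk set are event-free and uncensored when the case occurs: "they are still included in the study at that time, thus, eligible to experience the event now observed in the case". It adds that "individuals sampled as controls may subsequently become cases".

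The introduction says of combined treatment that "hepatotoxicity is the most frequent adverse effect that results in drug discontinuation", and it also describes "significant morbidity from treatment-related adverse events, such as hepatotoxicity, skin reactions, gastrointestinal, and neurological disorders". The Fluoroquinolones section presents these agents as second-line options after first-line hepatotoxicity.

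**The concern.** Intolerance of first-line drugs includes hepatotoxicity, and hepatotoxicity is the outcome. If the whole treatment course is open to view when eligibility is decided, an untimed exclusion for regimens changed because of intolerance can select on the outcome or its direct consequence.

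Two things are at stake. First, cases are lost: each DILI patient removed lowers the count that defines the primary outcome measure, in a study sized at 40 cases with no stated margin. Second, the odds ratio may be biased: its case side is distorted if leaving first-line drugs after DILI depends on the exposure. The Isoniazid section links slow acetylation to more severe hepatotoxicity, which makes such dependence conceivable, but the protocol does not link acetylator status to switching.

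There is also a conflict of method. Under risk-set sampling, membership at a given time depends only on what has happened up to that time. A whole-course exclusion makes it depend on what happens afterwards.

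**Working it through.** **Reading the text.** Take a patient who starts standard therapy, meets the DILI definition in week 8 (a week chosen only for illustration) and is moved to a regimen without first-line drugs. Inclusions 2 and 3 concern the initial regimen and are met. Exclusion 2 concerns the initial regimen and does not apply. Exclusion 3, read literally, does apply. Under Outcome measures the same patient is a case; under the risk-set rule the patient belongs in every risk set before week 8. The sections give opposite answers for one chart.

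The reach is limited. A patient restarted on first-line drugs is not caught. A patient who kept one of them may not be; the protocol notes that EMB is not regarded as hepatotoxic.

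**Reproducing the plan's figure.** Inputs (Sample size calculation): control exposure p0 = 0.50, odds ratio ψ = 3, correlation φ = −0.2, two controls per case, alpha 5%, power 80%.

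- Case exposure: p1 = 0.5×3/(1 + 0.5×2) = 0.75, as stated.
- Dupont's matched formula: n = [z(0.80)·√v(ψ) + z(0.975)·√v(1)]² / [e(1) − e(ψ)]², where e and v are the mean and variance per matched set of the exposed-case count given the number exposed.
- Result: 39.69, rounded up to 40 cases and 80 controls. Power at 40 is 80.3%. The sample size is right on its own inputs.

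**Case side (exclusion rates assumed).** Let se and su be the shares of exposed and unexposed DILI cases removed. The control odds are 0.5/0.5 = 1.

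- OR = 0.75(1 − se) / [0.25(1 − su)]
- Share lost = 0.75·se + 0.25·su
- Cases needed beforehand to keep 40 = 40/(1 − share lost), rounded up

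| se, su | OR | Lost | Left of 40 | Needed to keep 40 | Power if not replaced (true OR 3) |
|---|---|---|---|---|---|
| 0.30, 0.10 | 0.525/0.225 = 2.33 | 25% | 30 | 54 | 67% |
| 0.30, 0.30 | 0.525/0.175 = 3.00 | 30% | 28 | 58 | 64% |
| 0.10, 0.30 | 0.675/0.175 = 3.86 | 15% | 34 | 48 | 73% |

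The power column shows only the effect of fewer cases.

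**Control side, first risk set.** Future DILI switchers would also vanish from the controls. Assume a hazard ratio of 3, 50% exposed, and overall incidence of 5%, 11% or 28%. These are hepatotoxicity percentages in the introduction, used as planning values; the 11% stands in its sentence on drug discontinuation. The cumulative incidences F1 (exposed) and F0 (unexposed) are then 0.0745/0.0255, 0.163/0.057 and 0.402/0.158. With ge and gu the shares of exposed and unexposed non-DILI patients removed:

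control odds = [1 − se·F1 − ge(1 − F1)] / [1 − su·F0 − gu(1 − F0)]

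Example at 5%, se = 0.3, su = 0.1, ge = gu = 0: (1 − 0.02235)/(1 − 0.00255) = 0.980, and 2.33/0.980 = 2.38.

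| se, su; ge, gu | OR at 5% | 11% | 28% |
|---|---|---|---|
| 0.3, 0.1; 0, 0 | 2.38 | 2.44 | 2.61 |
| 0.3, 0.3; 0, 0 | 3.05 | 3.10 | 3.25 |
| 0.3, 0.1; 0.10, 0.05 | 2.50 | 2.55 | 2.68 |
| 0.3, 0.1; 0.05, 0.10 | 2.25 | 2.31 | 2.47 |

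Averaged over follow-up (constant hazards, numerical integration of the partial likelihood), the first row becomes 2.36, 2.39, 2.49 and the second 3.02, 3.05, 3.14.

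**Checking the fix.** Keep all patients, and assume that leaving for non-DILI reasons is independent of DILI risk given exposure and that no DILI follows. Censoring at departure returns 3.00 in every scenario. Without censoring the result is 2.90 to 2.92 (10% of exposed and 5% of unexposed leaving) or 3.07 to 3.08 (5% and 10%).

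**The case against.** The strongest reply is that a baseline-only meaning was intended. The list repeats itself elsewhere: normal liver function and consent each appear as both inclusion and exclusion. Overlap with inclusion 2 therefore does not prove that criterion 3 is about later changes, and two other exclusions also lack a time phrase. A study that counts DILI patients would hardly mean to discard them. All of this is fair, and it makes the clause ambiguous rather than plainly wrong. But the text does not state the benign meaning, and two abstractors could classify the same chart differently.

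The last words of the clause may also be an exception, sparing changes made within first-line drugs. That reading still catches the patient at issue, who was moved off those drugs.

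The affected group may be small, since nothing in the protocol describes switching at this clinic. That stands. So does the point that every exclusion rate above is assumed and that the range of odds ratios demonstrates a mechanism and estimates nothing. The return to 3.00 under censoring follows from the model's assumptions and shows only that the remedy is coherent.

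Detailed censoring rules may properly sit in a statistical analysis plan. Eligibility, however, is fixed here, and the eligibility wording is what creates the problem.

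**Conclusion.** The concern holds. As written, criterion 3 can exclude patients because of the primary outcome's consequences, and on that reading it contradicts the risk-set definition. It should be fixed; confidence is medium because a baseline-only intention cannot be ruled out.

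Case loss needs no assumption about exposure: any DILI patient removed is gone. Bias on the case side requires removal to differ by exposure; removing future switchers from the risk sets adds a smaller shift even when it does not. The illustrative odds ratios run from 2.25 to 3.86 around a true 3. They are not bounds, and the protocol supports neither a size nor a direction.

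**What to change.** - Apply criterion 3 only to regimens already modified at or before the first dose.
- State that a later regimen change, including one made because of DILI, does not exclude the patient. If baseline-only was always meant, these two sentences simply record it.
- For the analysis, censor event-free patients on the date they leave first-line drugs for reasons other than DILI, so that the planned risk sets remain valid.
- Report how many patients criterion 3 removes, and why.

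The cost is two eligibility sentences, one censoring sentence and one line in the patient flow, plus a few more charts to abstract with the date and reason for leaving first-line drugs. The 40/80 calculation does not change. Censoring assumes that leaving is unrelated to DILI risk given exposure. Switches for rising liver tests below the DILI threshold may break that assumption and should be counted separately. Nothing here alters clinical management.
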